2. LIST OF ABBREVIATIONS

Term	Definition / description		
AE	Adverse event		
AESI	Adverse event of special interest		
ALQ	Above limit of quantification		
ALT	Alanine aminotransferase		
AP	Alkaline phosphatase		
AST	Aspartate aminotransferase		
BI	Boehringer Ingelheim		
BIcMQ	BI customized MedDRA queries		
BLQ	Below the lower limit of quantification		
BMI	Body mass index		
CARE	Clinical data analysis and reporting environment		
CR	Clinical remission		
CRF	Case report form		
CTC	Common Terminology Criteria		
CTP	Clinical trial protocol		
CTR	Clinical trial report		
CV	Arithmetic coefficient of variation		
DNA	Deoxyribonucleic acid		
ECG	Electrocardiogram		
eCRF	Electronic case report form		
EMA	European Medicines Agency		
EOS	End of Study		
EOT	End of treatment		
ES	Enrolled set		
EudraCT	European union drug regulating authorities clinical trials		
F/U	Follow-up		
ICH	International Council for Harmonisation of Technical Requirements for Pharmaceuticals for Human Use		
IL	Interleukin		

TSAP for BI Trial No: 1368-0007 Page 6 of 29
Proprietary confidential information © 2022 Boehringer Ingelheim International GmbH or one or more of its affiliated companies

Term	Definition / description		
IPD	Important protocol deviation		
LLOQ	Lower limit of quantification		
LOCF	Last observation carried forward		
LOQ	Limit of quantification		
MedDRA	Medical Dictionary for Regulatory Activities		
NOA	Not analysed		
NOR	No valid result		
NOS	No sample available		
OC	Observed cases		
OC-IR	Observed cases including values after rescue medication		
OR	Original results		
PT	Preferred Term		
Q1	1 st quartile		
Q3	3 rd quartile		
RAGe	Report appendix generator		
RCTC	Rheumatology Common Toxicity Criteria		
REP	Residual effect period		
SAE	Serious adverse event		
SAF	Safety Analysis Set		
SD	Standard deviation		
SDL	Subject data listing		
SMQ	Standardised MedDRA query		
SOC	System Organ Class		
TSAP	Trial statistical analysis plan		
ULN	Upper limit of normal range		
ULOQ	Upper limit of quantification		

3. INTRODUCTION

As per ICH E9, the purpose of this document is to provide a more technical and detailed elaboration of the principal features of the analysis described in the protocol, and to include detailed procedures for executing the statistical analysis of the primary and secondary variables and other data.

This TSAP assumes familiarity with the Clinical Trial Protocol (CTP), including Protocol Amendments. In particular, the TSAP is based on the planned analysis specification as written in CTP Section 7 "Statistical Methods and Determination of Sample Size". Therefore, TSAP readers may consult the CTP for more background information on the study, e.g., on study objectives, study design and population, treatments, definition of measurements and variables, and planning of sample size.

The statistical analyses will be performed within the validated working environment CARE, including SASTM (current Version 9.4, by), and a number of SASTM-based tools (e.g., macros for the analyses of AE data or laboratory data; Report Appendix Generator system (RAGe) for compilation/formatting of the CTR appendices).

This statistical analysis plan describes the final analysis of this discontinued trial.

4. CHANGES IN THE PLANNED ANALYSIS OF THE STUDY

As a consequence of the early termination of this open-label, long-term extension trial, the following changes in the planned analyses have been implemented:

1) Due to limitations in the data capture of the current eCRF, the secondary endpoints specified in the protocol, "Proportion of patients with perianal fistula remission at weeks 48, 96, 144, 192, 240, 288, and 336" and "Proportion of patients with perianal fistula response at weeks 48, 96, 144, 192, 240, 288, and 336", cannot be fully derived, and thus the planned analyses for these secondary endpoints cannot be performed. A listing at the individual patient level showing the status of fistulas for each treated patient will instead be prepared.

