Fistula relapse is suspected if ≥ 1 external fistula orifice re-emerges, which was open at baseline or newly emerged during the preceding trial but was closed at completion of the parent study or at any time during the current trial; or which emerged newly. Fistula relapse is confirmed in a second independent visit ([Flowchart 2B](#)).

A patient with a confirmed fistula relapse will receive a single i.v. infusion of 1200mg spesolimab. At week 4 after the single i.v. infusion dose, patients will continue with an intensified subcutaneous spesolimab maintenance dosing of 600mg q4W, as seen in [Figure 3.1:2](#). An additional visit has to be planned at week 12 after the single i.v. infusion to check the patient's response status. For patients with fistula relapse, this week 12 assessment will include clinical assessment, [REDACTED] and MRI, which will guide investigator judgment of patient response status.

Luminal inflammatory flare, is defined as an increase in PRO-2 score [sum of 7-day weighted stool frequency (SF) and abdominal pain (AP) , components of the [REDACTED], using the original [REDACTED] multiplying factors of 2 for SF and 5 for AP] by >50 points from baseline of the current trial, plus an increase in [REDACTED] score by ≥ 100 points from baseline of the current trial with an absolute [REDACTED] >220 in a second independent confirmation visit, with an absolute [REDACTED], in absence of enteric pathogens in stool. In case of a suspected inflammatory flare, the site will ask the patient to immediately start entering his [REDACTED] symptom score data into the eDiary until the next scheduled or unscheduled visit at which a flare confirmation assessment will be performed, and then to continue entering the data as planned (i.e. for 10 days before each visit).

A patient with a luminal inflammatory flare (endoscopically confirmed) without fistula relapse might be treated as per SOC based on clinician judgement while continuing the same spesolimab maintenance dose according [flow chart 2A](#). After 12 weeks of flare confirmation (visit F3) a new rectoscopy/proctoscopy and [REDACTED] assessment will be performed to assess luminal flare response to SOC as per investigator judgement. For details of trial procedures, please follow the [Flow chart 2A](#).

Figure 3.1:2 Trial design in case of fistula relapse

[figure not shown]

Figure 3.1:3 Trial design in case of luminal inflammatory flare

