8.3.1 Source documents

In accordance with regulatory requirements, the investigator should prepare and maintain adequate and accurate source documents and trial records that include all observations and other data pertinent to the investigation on each trial patient. Source data as well as reported data should follow the "ALCOA principles" and be attributable, legible, contemporaneous, original and accurate. Changes to the data should be traceable (audit trail).

Data reported on the CRF must be consistent with the source data or the discrepancies must be explained.

The current medical history of the patient may not be sufficient to confirm eligibility for the trial and the investigator may need to request previous medical histories and evidence of any diagnostic tests. In this case, the investigator must make at least one documented attempt to retrieve previous medical records. If this fails, a verbal history from the patient, documented in their medical records, would be acceptable.

Copies of source documents will be provided to the Sponsor. Before sending or uploading those copies, the investigator must ensure that all patient identifiers (e.g. patient's name,

initials, address, phone number, social security number) have properly been removed or redacted from any copy of the patients' source documents.

If the patient is not compliant with the protocol, any corrective action e.g. re-training must be documented in the patient file.

For the CRF, data must be derived from source documents, for example:

- Patient identification: gender, year of birth (in accordance with local laws and regulations)
- Patient participation in the trial (substance, trial number, patient number, date patient was informed)
- Dates of patient's visits, including dispensing of trial medication
- Medical history (including trial indication and concomitant diseases, if applicable)
- Medication history
- Adverse events and outcome events (onset date (mandatory), and end date (if available))
- Serious adverse events (onset date (mandatory), and end date (if available))
- Concomitant therapy (start date, changes)
- Originals or copies of laboratory results and other imaging or testing results, with proper documented medical evaluation (in validated electronic format, if available)
- Completion of patient's participation in the trial" (end date; in case of premature discontinuation document the reason for it).

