5.2.2 Secondary endpoints

- Proportion of patients with perianal fistula remission at week 48, 96, 44, 192, 240, 288, and 336
- Proportion of patients with perianal fistula response at week 48, 96, 44, 192, 240, 288, and 336

Please refer to Table 2.1:1 of the CTP for a complete description of the secondary endpoints.

As described in Section 4, due to limitations in the CRF collection of data, it is not feasible to calculate either of these two secondary endpoints. Nonetheless, the derivation algorithms for these two endpoints, as originally proposed, are maintained and described below.

The derivations of perianal fistula remission and response are Boolean functions based on the following, where a fistula refers to an external opening:

Let

- ν indicate a given analysis visit;
- o(v) indicate the count of open fistulas (\pm drainage/discharge upon gentle finger compression) at v;
- $\epsilon(v)$ be the number of newly emerged fistulas (\pm drainage/discharge upon gentle finger compression) from the baseline of the parent trial to v;
- BL be the number of open and draining fistulas at the baseline of the parent trial.

Then, perianal fistula remission (PFM) for a given patient x is

$$PFM(x) = \begin{cases} 0, & if \frac{o(v)}{BL + \epsilon} > 0\\ 1, & if \frac{o(v)}{BL + \epsilon} = 0 \end{cases}$$

, and perianal fistula response (PFR) for a given patient x is

$$PFR(x) = \begin{cases} 0, & if \frac{o(v)}{BL} > 0.5\\ 1, & if \frac{o(v)}{BL} \le 0.5 \end{cases}$$

TSAP for BI Trial No: 1368-0007 Page 10 of 29
Proprietary confidential information © 2022 Boehringer Ingelheim International GmbH or one or more of its affiliated companies

TSAP for BI Trial No: 1368-0007 Page 11 of 29
Proprietary confidential information © 2022 Boehringer Ingelheim International GmbH or one or more of its affiliated companies

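### Should SAP Section 4 have named the eCRF gap and searched source documents before giving up both secondary endpoints?

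*SAP*

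**What the plan says.** SAP Section 4 introduces its changes with "As a consequence of the early termination of this open-label, long-term extension trial, the following changes in the planned analyses have been implemented". Its first item begins "Due to limitations in the data capture of the current eCRF, the secondary endpoints specified in the protocol" and states that remission and response at weeks 48 to 336 cannot be completely derived. The replacement is stated as "A listing at the individual patient level showing the status of fistulas for each treated patient will instead be prepared".

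SAP Section 5.2.2 repeats that "it is not feasible to calculate either of these two secondary endpoints" but keeps the derivation formulas. Sections 6.6.2 and 7.5.2 give the same reason. SAP Section 7 adds a second ground: because of early termination and the use of an abbreviated trial report, part of the planned analysis will not be done. The history table (SAP Section 10) dates this version 28 October 2022, after the decision to stop and before final database lock.

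In the protocol, Table 2.1:1 defines both endpoints by closure and absence of drainage on gentle compression. Section 3.1 suspects a relapse when an "external fistula orifice re-emerges, which was open at baseline or newly emerged during the preceding trial"; such an opening must have healed over in the meantime, and a wholly new one also counts. Section 8.3.1 requires "source documents and trial records that include all observations and other data pertinent to the investigation on each trial patient" and adds: "Copies of source documents will be provided to the Sponsor".

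**The concern.** The reason is thin for what it removes. These two endpoints are the only secondary endpoints, and they carry the second main objective, long-term efficacy. Early termination accounts for visits that never took place. It does not, by itself, account for visits that did.

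A gap in the eCRF need not be a gap in the trial's records. A site applying the relapse rule has to know which openings had closed and which are new. Source documents are meant to be complete, and the database was still open. On this reading the counts should exist somewhere and the plan does not look for them.

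Two things are at stake: a public results summary (Protocol Section 8.6) with no efficacy proportion, and a reader who cannot exclude that efficacy was dropped because it looked poor.

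**Working it through.** The plan gives no figure to reproduce. Protocol Sections 7.1 and 7.5 say that there is no hypothesis test and no sample size calculation. The check has four parts.

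**1. What could be recovered, by date.** Inputs: protocol date 28 Nov 2019 (synopsis); SAP version date 28 Oct 2022; visit days 337, 673, 1009 and 1345 for weeks 48, 96, 144 and 192 (Flow Charts 1A and 1B). Latest first dose = 28 Oct 2022 − (visit day − 1).

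| Week | Days subtracted | Latest first dose |
|---|---|---|
| 48 | 336 | 26 Nov 2021 |
| 96 | 672 | 25 Dec 2020 |
| 144 | 1008 | 24 Jan 2020 (57 days after the protocol date) |
| 192 | 1344 | 22 Feb 2019 (279 days before the protocol date) |

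The ±7-day visit window moves each date one week later and changes nothing. The SAP date is not a last-visit date, but a week-192 visit would have to fall at least 279 − 7 = 272 days after it. SAP Section 7.7 also stops its exposure categories at 144 weeks. So weeks 192, 240, 288 and 336 are empty for a reason unrelated to the eCRF: 2 × 4 = 8 of 2 × 7 = 14 planned proportions. At most 2 × 3 = 6 remain, and week 144 is doubtful.

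**2. Size of a source search.** With 20 patients (Protocol Section 7.5), at most 20 × 3 = 60 patient-visits, or 20 × 2 = 40 if nobody reached week 144. Twenty is a planned number; Protocol Section 3.1 allows patients from other trials to raise it.

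**3. What the endpoints need, against what the protocol makes sites record.** By the SAP formulas, with a parent baseline count BL of at least 1, remission is 1 exactly when the open count o(v) is 0. Response is 1 when o(v)/BL ≤ 0.5. Both need the number of open openings at the scheduled visit, and the protocol definition also needs drainage status.

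- The relapse rule in Protocol Section 3.1 contains no drainage element.
- It is met by a single opening, so it does not force a count of the rest.
- It does not instruct sites to document every opening at weeks 48, 96 and 144.
- Protocol Section 8.3.1 is general wording on source documents and does not mention fistula counts.

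Records good enough to apply the relapse rule can therefore still be too poor for the endpoints.

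**4. What a recovered proportion would tell.** Exact (Clopper-Pearson) 95% intervals for assumed counts: 6/20 = 30% (12% to 54%); 10/20 = 50% (27% to 73%); with only ten evaluable, 5/10 = 50% (19% to 81%). Visits with incomplete records would be excluded, so the denominator would depend on how well each site happened to document drainage.

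**The case for a change.** The best counter-argument is that the SAP's own formulas ask for little. Remission needs only whether any opening is open, response adds one number from the parent trial, and the plan still intends to list fistula status for every treated patient. If status can be listed, it is fair to ask why nothing can be counted. Reviewing at most 60 patient-visits is also not a heavy burden.

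Part of this stands. The visible text does not identify the missing item, and one sentence doing so would help the reader. It does not show that the counts are obtainable. The SAP's wording suggests that some information is present but not enough for a complete derivation, which fits a status listing without a reliable count.

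Termination and the eCRF reason also fit together better than they first appear. The SAP speaks of the current eCRF, and a form that would have been revised in a continuing trial may sensibly be left alone in a stopped one. That is an inference, but the abbreviated-report ground in SAP Section 7 supports it. SAP Section 7.3 also cites Section 4 for a statement on treatment compliance that the public Section 4 does not contain, so silence there is weak evidence that nothing was checked.

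The suspicion of selective omission cannot be ruled out from the documents, but little supports it. The stopping reason concerns the parent trial. The change is declared before lock and repeated in four places, the formulas are retained, and the individual data are displayed.

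The protocol and SAP definitions do differ for an opening that was present but not draining at parent baseline: the SAP counts it if open, while the protocol's remission definition does not. That has no effect while neither endpoint is calculated.

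**Conclusion.** No change to the plan is called for. The unnamed eCRF item is a gap in documentation that the trial report can close in a sentence, and closing it changes no result. A retrospective, opening-by-opening search of source documents is the only step that could change a result. It is a trade-off without demonstrated gain: at most 6 of 14 proportions, an interval about 46 percentage points wide at 10/20, denominators shaped by uneven recording of drainage, and a possible delay to database lock. In a stopped, single-arm, descriptive trial planned for up to 20 patients, a listing for each treated patient conveys nearly as much, and a reader can count from it whatever is countable.

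This rests on three assumptions: that enrolment stayed near 20, that no patient reached week 192 (supported by the dates and by the exposure categories in SAP Section 7.7), and that the listing shows fistula status in usable detail. Evidence that sites had recorded every opening with its drainage at the scheduled visits would reopen the question. The documents contain none.

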5. ENDPOINTS

For handling of missing data see Section 6.6, unless otherwise specified.

Note that, unless otherwise stated in Section 7, for the specification of efficacy endpoints below, the baseline is defined as the last non-missing value reported prior to the first dose of the study drug in the preceding induction study, i.e., the efficacy baseline definition from the parent trial.

For the summary of all efficacy data, only those observations which were collected during the on-treatment period (i.e. first dose of spesolimab through to the last dose of spesolimab + 16 weeks) will be used.

5.1 PRIMARY ENDPOINT

The primary endpoint for this trial is a safety endpoint: the exposure-adjusted incidence rate of patients reporting a treatment emergent adverse event (TEAE) up to week 336 of the maintenance treatment. For this endpoint, time-at-risk begins at the study drug start date of the current study, and not of the parent trial.

Please refer to Section 7.2.2 of the CTP for a more thorough discussion of the primary endpoint.

5.2 SECONDARY ENDPOINTS

5.2.1 Key secondary endpoints

Not applicable. No key secondary endpoints have been specified for this trial.

5.2.2 Secondary endpoints

- Proportion of patients with perianal fistula remission at week 48, 96, 44, 192, 240, 288, and 336
- Proportion of patients with perianal fistula response at week 48, 96, 44, 192, 240, 288, and 336

Please refer to Table 2.1:1 of the CTP for a complete description of the secondary endpoints.

As described in Section 4, due to limitations in the CRF collection of data, it is not feasible to calculate either of these two secondary endpoints. Nonetheless, the derivation algorithms for these two endpoints, as originally proposed, are maintained and described below.

The derivations of perianal fistula remission and response are Boolean functions based on the following, where a fistula refers to an external opening:

Let

- ν indicate a given analysis visit;
- o(v) indicate the count of open fistulas (\pm drainage/discharge upon gentle finger compression) at v;
- $\epsilon(v)$ be the number of newly emerged fistulas (\pm drainage/discharge upon gentle finger compression) from the baseline of the parent trial to v;
- BL be the number of open and draining fistulas at the baseline of the parent trial.

Then, perianal fistula remission (PFM) for a given patient x is

$$PFM(x) = \begin{cases} 0, & if \frac{o(v)}{BL + \epsilon} > 0\\ 1, & if \frac{o(v)}{BL + \epsilon} = 0 \end{cases}$$

, and perianal fistula response (PFR) for a given patient x is

$$PFR(x) = \begin{cases} 0, & if \frac{o(v)}{BL} > 0.5\\ 1, & if \frac{o(v)}{BL} \le 0.5 \end{cases}$$

TSAP for BI Trial No: 1368-0007 Page 10 of 29
Proprietary confidential information © 2022 Boehringer Ingelheim International GmbH or one or more of its affiliated companies

TSAP for BI Trial No: 1368-0007 Page 11 of 29
Proprietary confidential information © 2022 Boehringer Ingelheim International GmbH or one or more of its affiliated companies

6. GENERAL ANALYSIS DEFINITIONS

6.1 TREATMENT(S)

For basic study information on treatments to be administered, assignment of treatment groups, and selection of doses, refer to CTP Section 4.

Patients who experience a fistula relapse during the maintenance treatment (as defined in CTP Table 2.1: 1) will be administered a single intravenous dose of spesolimab 1200 mg followed by an intensified subcutaneous maintenance dosing schedule with 600 mg q4w.

The following study periods are defined:

Table 6.1: 1 Flow chart of analysis periods which apply to all patients.

Analysis period	On-/off- treatmen t	Start (included)	End (included)
Screening period (Approx 1-2wks)	Off- treatment	Earliest of (Date of informed consent, first screening procedure)	Date/time of injection of first s.c. maintenance study drug minus 1 minute.
Overall maintenance period ¹ (Approx 336 wks)	On- treatment	Date/time of first s.c. maintenance study drug.	Date of last administered spesolimab (irrespective of formulation) + 112 days at 11:59pm.
Follow-up period ²	Off- treatment	Date of last study drug administration (irrespective of formulation) + 113 days at 12:00 AM.	Latest of: i) Date of EOS visit (Week 352 visit); ii) last contact date on End of Study page at 11:59 p m.

Dates are defined individually per patient. If more than one date is associated with a specific visit, measurements associated with a specific date are assigned to a study analysis phase according to the rules specified in the table. An analysis phase will not extend beyond the start date of the following phase.

The on-treatment period is defined as the overall maintenance period (including REP).

For all analysis periods, assessments done on the same day as the first maintenance treatment dose will be assigned to the appropriate analysis phase based on the assessment of date/time. If time is not collected for an assessment, then assignment will be to the previous analysis phase, e.g., to the screening phase.

Treatment Labels

Treatments will be labelled as follows:

"Overall Speso"

¹ The overall maintenance treatment period applies to all patients taking at least one dose of maintenance treatment regardless of flare occurrence. This period will be considered to understand long-term efficacy and safety of spesolimab.

² The follow-up period only exists if the trial completion date is after the date of end of last injection/infusion plus REP.

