5.2.2 Vital signs

Vital signs evaluations will be performed at visits as shown in the [Flow Chart](#). This includes body temperature, pulse rate, systolic/diastolic blood pressure and respiratory rate. Respiratory rate, pulse rate, and blood pressure will be measured after patients have been sitting comfortably for at least five minutes. Measurement of vital signs should precede blood sampling to avoid the impact of blood sampling on the vital sign measurements. At dosing visits, vital sign evaluations will be performed pre-dose for both visits with i.v. and s.c. administration of study drug. At s.c. dosing visits, vital signs will be assessed at approximately 10 minutes after study drug administration. Also, at visit M1 and visit M2 (s.c. dosing visits) additional vital signs assessments will be performed approximately 60 minutes post-dose (i.e. 60 min. after last injection). At visits with i.v. dose administration, vital sign evaluations will be performed pre-dose and additional evaluations will be taken at 5 and 60 minutes post-dose

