Description of change 9		Reorganisation of information on concomitant treatments. Inclusion of stable doses of anti-TNF as allowed concomitant treatment during the study. Clarifications on steroids and antibiotics treatment and allowed surgeries. Inclusion of approved medications to treat moderate-to-severe luminal inflammatory flares as concomitant therapy in patients with fistula response but who present luminal flare.
Rationale for change		Clarify use of concomitant treatments. To align with new eligibility criteria in parent trial 1368.8, which allows stable doses of anti-TNF therapy

	
(SOC for luminal inflammatory activity control in CD patients).
 
UC spesolimab phase II program data does not support use of spesolimab in luminal inflammatory flare. Thus, patients who present with luminal inflammatory flare while maintaining fistula response will be treated with SOC.

Section to be changed	Section 5.2.2.
Description of change 10	Inclusion of additional vital signs measurement at visit 1 at M1 post dose.
Rationale for change	Include safety measure after two first subcutaneous doses.
Section to be changed	Table 5.2.3: 1
Description of change 11	Include clarifications in some labs: HbA1c, TSH. Delete bicarbonate and fecal lactoferrin.
Rationale for change	Clarification of when to test some parameters and deletion of parameters that are not relevant for the disease.
Section to be changed	Section 5.4.1
Description of change 12	[REDACTED]
[REDACTED]	[REDACTED]
Section to be changed	Section 5.4.2
Description of change 13	Include when the rectal biopsies should be done
Rationale for change	Clarification.
Section to be changed	Section 5.5 and 6.2.1
[REDACTED]	[REDACTED]
Section to be changed	Section 10.6
Description of change 15	Delete appendix.
Rationale for change	No needed for this indication.

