6.7 BASELINE, TIME WINDOWS AND CALCULATED VISITS

Measurements reported with date and time and taken prior to the start of administration of trial treatment are pre-treatment values. Measurements reported with a date only (and no time) and taken on the day of first administration of trial treatment are assigned as pre-treatment values. These pre-treatment values will be assigned to visits according to the nominal visit number as recorded on the eCRF or as provided by the laboratory.

Refer to Section 5.2 for baseline definitions for each applicable efficacy endpoint in this trial.

For safety endpoints, the baseline is defined as the last value prior to initiation of the maintenance treatment (Visit M1).

Analysis of AE data, concomitant medication or non-drug therapies will not be based on visits. Therefore, no assignment to time windows will be necessary.

Only one observation per time window will be selected for statistical analysis at a particular visit – the value which is closest to the protocol planned visit day will be selected. If there are two observations which have the same difference in days to the planned day, but which are not measured on the same day, the later value will be selected. If there are two observations on the same day, the later value will be selected.

For derivation of the last value on treatment, minimum value on treatment, and maximum value on treatment, all on-treatment values (whether selected in any time window or not; see Table 6.1: 1 for definition of the on-treatment period) will be considered. These will be derived for analysis of laboratory and vital signs data. For identification of potentially clinically significant abnormal laboratory values, all values (whether selected in any time window or not) within the on-treatment period will be considered.

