7.8.1 Adverse events

AEs will be coded with the most recent version of MedDRA.

The analysis of AEs will be descriptive in nature. All analyses of AEs will be based on the number of patients with AEs and not on the number of AEs. System organ classes (if applicable) will be sorted according to the standard sort order specified by the EMA. Preferred terms (if applicable) will be sorted by total frequency (within system organ class).

For further details on summarization of AE data, please refer to "Analysis and Presentation of Adverse Event Data from Clinical Trials" (4) [KM Asset BI-KMED-BDS-HTG-0041] and "Handling of missing and incomplete AE dates" (3) [KM Asset BI-KMED-BDS-HTG-0035].

The analysis of AEs will be based on the concept of treatment emergent AEs. This means that all AEs will be assigned to either the screening period, the applicable on-treatment period, or the off-treatment period (i.e. follow-up) as defined in Section 6.1. Since only the start date of an AE is collected (without start time), any AE which occurs on the same day as the first maintenance treatment will be assigned to the respective on-treatment period.

Refer to CTP Section 7.2.2 for a description of the calculation of exposure-adjusted adverse event incidence rates (per the primary endpoint).

The AE summaries described below will be produced for the following treatment periods:

• The overall maintenance period [based on the SAF]

An overall summary of AEs will be presented. This overall summary will include the class of AESIs. Refer to CTP Section 5.2.6.1.4 for a description of what is considered as an AESI.

The investigator identified AESI will be captured from the eCRF and reported in the "Investigator reported AESI" table. In addition, user defined adverse event categories (UDAEC) identified through specific search criteria will be reported separately; the UDAEC applicable to this trial are stored centrally and will be referenced for this presentation.

Adverse Events classified as 'other significant' will be reported using an adaptation of the ICH E3 (6) and will include those non-serious and non-significant AEs which were reported with 'action taken = drug withdrawn' or 'action taken = reduced'.

Table 7.8.1: 1 Project MEDDRA search criteria for User Defined Adverse Events Categories (UDAEC)

User-defined AE category			
Label	Description		
Infections ALL	Combined search strategy based on the individual UDAECs for infections described below		

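### SAP 6.1 and 6.7 class any untimed first-dose-day reading as pre-treatment, with no exception for M1 vital signs that are post-dose by schedule

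*SAP*

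**What the plan says.** SAP 6.1 divides each patient's follow-up into an off-treatment screening period, an on-treatment overall maintenance period and an off-treatment follow-up period. Its main rule for the first-dose day uses the clock: "assessments done on the same day as the first maintenance treatment dose will be assigned to the appropriate analysis phase based on the assessment of" date and time. The fallback follows: "If time is not collected for an assessment, then assignment will be to the previous analysis phase, e.g., to the screening phase". SAP 6.7 says the same of measurements "reported with a date only (and no time) and taken on the day of first administration of trial treatment are assigned as pre-treatment values".

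SAP 6.7 also defines the safety baseline as the last value before maintenance treatment starts at M1. It derives the last, minimum and maximum values on treatment, for laboratory and vital-signs data, from on-treatment values only. For choosing one value per visit window it adds: "If there are two observations on the same day, the later value will be selected".

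Protocol 5.2.2 and flow chart footnote 3 require vital signs before dosing at every dosing visit and about 10 minutes after each s.c. dose. At M1 and M2, "additional vital signs assessments will be performed approximately 60 minutes post-dose" as well. Global Amendment 2 gives the reason for the added reading: "Include safety measure after two first subcutaneous doses".

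Adverse events have their own rule in SAP 7.8.1. Because no start time is collected for them, "any AE which occurs on the same day as the first maintenance treatment will be assigned to the respective on-treatment period".

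**The concern.** The fallback suits measurements made before dosing, such as the scheduled laboratory samples. It is written for every first-dose-day measurement, however, and so also covers vital signs that the schedule places after the injection. An untimed reading at 10 or 60 minutes would be filed under screening even though its planned time point shows that the patient had already been dosed.

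Two things are at stake. The readings closest to first exposure, one of them added expressly as a safety measure, would be missing from the on-treatment extremes. And if such a reading were taken as baseline, a first-dose effect would be built into the reference value and would shift every later change from baseline for that patient. Protocol 7.2.5 intends vital signs to be compared with findings from before treatment began.

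**Working it through.** The plan gives no figure for this point, so the check is a trace of the rules, followed by a count.

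**Inputs.** Vital-signs sets at M1: one pre-dose, one at about 10 minutes, one at about 60 minutes (Protocol 5.2.2). Planned patients: up to 20 (Protocol 7.5). Assignment rules: SAP 6.1 and 6.7.

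**Trace for one patient at M1**

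| M1 set | Clock time recorded | No clock time |
|---|---|---|
| Pre-dose | pre-treatment | pre-treatment |
| About 10 min post-dose | on-treatment | pre-treatment |
| About 60 min post-dose | on-treatment | pre-treatment |

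With times, the split is 1 pre-treatment and 2 on-treatment, as it should be. Without times it is 3 and 0.

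**Consequence that follows directly.** An untimed post-dose M1 set is off-treatment. It therefore cannot enter the on-treatment last, minimum or maximum, whichever record serves as baseline.

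**Consequence that is only possible.** Once all three sets are labelled pre-treatment, the 60-minute set can be read as the last of them. The SAP does not say how untimed same-day values are ordered. Its same-day rule favours the later value, but it is written for visit windows and not for baseline.

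**Count.** Suppose n patients are treated and k of them had their first dose under the current protocol version. Assume that the 10-minute reading was already required before Global Amendment 2 and the 60-minute reading was not. The ceiling is then n + k sets:
- n = 20, k = 20: 20 + 20 = 40 sets.
- n = 20, k = 0: 20 + 0 = 20 sets.
- All times recorded: 0 sets.

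The documents give neither n nor k.

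**Size of a baseline shift, if one occurred.** Let d be the post-dose reading minus the pre-dose reading. Using the post-dose reading as baseline changes every later difference by −d. Take invented systolic values of 120 mmHg pre-dose, 95 at 60 minutes and 118 at M2:
- Correct change at M2: 118 − 120 = −2.
- Change with the 60-minute reading as baseline: 118 − 95 = +23.
- Check: d = 95 − 120 = −25, and −2 − (−25) = +23.

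The 95 would also be absent from the on-treatment minimum.

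**The case against.** The strongest reply is that the premise is not shown. Nothing says that vital signs are recorded without times, and the text leans the other way. The main rule in SAP 6.1 works by date and time, screening ends one minute before the first injection, and Protocol 5.2.2 sets readings at minutes after dosing. Where times are not collected, for adverse events, SAP 7.8.1 says so. This stands, and it makes the point conditional. It does not remove it: SAP 6.7 turns on how a value is reported, so one record with a missing time is enough to trigger the fallback.

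A reader might infer that the 60-minute reading becomes the baseline. The documents do not support that. A record labelled post-dose does not, on its face, precede the start of treatment, and the SAP gives no ordering for untimed values. The outcome is open, not determined.

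A reader might also see the adverse-event rule as a contradiction. It is not one. Adverse events lack start times by design, and counting same-day events as on-treatment is the cautious choice for them. The comparison shows only that a data type can be given its own default.

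Safeguards also limit the harm. SAP 7 lists all individual values, including those from off-treatment periods, so the reading would remain visible. Protocol 5.2.6.1.1 has clinically relevant vital-sign changes recorded as adverse events, and those on the first-dose day count as on-treatment.

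Finally, the public SAP text contains no vital-signs analysis section, and the trial is reported in abbreviated form after early termination. Whether a change-from-baseline table is produced, or whether planned time points are handled elsewhere, cannot be checked. SAP 6.7 does still commit to the on-treatment vital-signs derivations.

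**Conclusion.** The point holds as a gap in the assignment rule, not as a demonstrated error in the data. Whenever an M1 vital-signs record at about 10 or 60 minutes lacks a clock time, the SAP as written classes it wrongly and removes it from the on-treatment last, minimum and maximum. Its use as safety baseline is possible but not certain.

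The range is 0 to at most 40 sets in 20 patients. The true ceiling is probably lower, because the trial stopped early and any patient first dosed before Global Amendment 2 would not have had the 60-minute reading scheduled. It would be wrong to read the rule as showing that two of every three M1 sets are misassigned; that needs the assumption that no vital-sign times were collected, which the documents neither state nor exclude.

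The reach is narrow. Only M1 records are misclassified; later visits are touched only through an affected baseline. Scheduled laboratory samples are taken before dosing, so the default is right for them.

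**What to change.** In SAP 6.1, and in the matching sentence of 6.7, state that first-dose-day records without a clock time are assigned by planned time point: pre-dose to screening and baseline, post-dose to the overall maintenance period. Restrict the safety baseline to pre-dose records. Keep the previous-phase default only for records with neither a time nor a planned time point.

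The cost is a sentence or two in the SAP and one programming condition on the planned time point, with no new data and no extra procedure. SAP version 2.0 was itself written before final database lock, which is the natural point for such a change. Checking whether the eCRF captures vital-sign times, and whether any M1 times are missing, would show at once if any record is affected. If none is, the added wording changes no result.
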